7.2 Safety definitions

Adverse Event (AE)

Any untoward medical occurrence in a patient or other clinical investigation participant taking part in a trial of a medical device, which does not necessarily have to have a causal relationship with the device under investigation.

An AE can therefore be any unfavourable and unintended sign (including an abnormal laboratory finding), symptom or disease temporally associated with the use of the device, whether or not considered related to the device.

Serious Adverse Event

A serious adverse event is any untoward medical occurrence that:

- results in death
- is life-threatening
- requires inpatient hospitalisation or prolongation of existing hospitalisation
- results in persistent or significant disability/incapacity
- consists of a congenital anomaly or birth defect.

Other 'important medical events' may also be considered serious if they jeopardise the participant or require an intervention to prevent one of the above consequences.

NOTE: The term "life-threatening" in the definition of "serious" refers to an event in which the participant was at risk of death at the time of the event; it does not refer to an event which hypothetically might have caused death if it were more severe.

7.3 Procedures for recording adverse events

All SAEs need to be reported to the sponsor/host Trust R&D within one working day of the investigator team becoming aware of them – AEs should be reported on within two weeks of becoming aware of them. For this purpose an AE report form is completed by the researcher and/or Chief Investigator

The relationship of each adverse event to the trial must be determined by the Chief Investigator, a medically qualified individual, according to the following definitions:

- Related: The adverse event follows a reasonable temporal sequence from swabbing. It cannot reasonably be attributed to any other cause.
- **Not Related**: The adverse event is probably produced by the participant's clinical state or by other modes of therapy administered to the participant.
- Severity grading: the Chief Investigator will also record if it concerns an AE or SAE.

This is recorded on the aforementioned AE reporting form. The forms are stored in the study site file.

Pseudo-anonymised copies of all adverse events forms will be shared with Milliken as soon as causality reporting has been performed and concluded.

8. STATISTICAL CONSIDERATION AND DATA ANALYSIS PLAN

8.1 Analysis of baseline characteristics

To determine the demographics and characteristics of the patients in the two arms the following data will be collated:

- Age (yrs)
- Gender
- Height (kg), weight (cm), BMI

Data concerning the actual osteotomy procedure will also be collected, including:

- Type of surgery
 - o Including type of medical device used and which leg operated on
- Length of operation (min) and blood loss (ml) during operation
- Type of anaesthetic and analgesics prescribed post-surgery
- Hospital length of stay (days)
- Moment physiotherapy and early recovery initiated
- Type of standard bandaging applied if control patient.

Any differences in distribution will be established with Chi-squared test or Mann-Whitney U-test/t-test (depending on distribution of data) as indicated.

8.2 Primary outcome statistics

To determine the level of operation-site related pain experienced at day 5 post-operation and to compare the average pain scores of patients in the control and Andoflex TLC Calamine Lite arm respectively, through administration of 10 cm visual descriptor scale (VDS) for pain.

Confidential – This document and the information contained herein may not be reproduced, used or disclosed without written permission from North Cumbria Integrated Care NHS Foundation Trust Page | 18

The study is powered to detect the established minimal clinically important difference (MCID) of 1.5 cm on a 10 cm VDS pain.

The average difference between time points will be calculated per group, 5 days post-surgery weeks being the primary endpoint. Three days, 12 days and 6 weeks post-surgery will also be analysed. To compare the groups, the Mann-Whitney U-test will be applied.

To avoid relying on one outcome measure related to pain, at 3, 5, 12 days, and 6 weeks post-surgery pain perception will also be measured using the short form McGill pain questionnaire. Again, to compare groups the Mann-Whitney U-test will be applied.

8.3 Secondary outcome statistics

The average baseline demographics for participants in each group will be compared to ascertain that randomisation has indeed led to comparable distribution of participants:

Sex, age, height, weight, BMI, length of stay, type of anaesthetic for surgery and type of analgesics post-surgery.

To compare outcomes between the two groups (standard vs Andoflex TLC Calamine Lite bandaging), student t-test, Mann-Whitney U-test or Chi-squared test will be applied as applicable, depending on type and distribution of data .

Cox proportional hazards regression analysis will be conducted to investigate the role of bandaging and other covariates (as mentioned above) in post-surgery related pain and knee function.

The statistics apply to:

Up to 12 weeks prior to surgery, and 12 weeks post-surgery, knee function and quality of life measurements: Knee and Osteoarthritis Outcome Score (KOOS), and range of movement of the affected limb (goniometer)

Descriptive safety overview at 30 days and 12 weeks post-surgery:

- Readmitted to theatre and/or hospital
- Infection of wound site
- Diagnosed with pulmonary embolism or deep vein thrombosis
- All monitored remotely by review of patients' hospital notes.

Patient satisfaction survey at 12 days post-surgery – any difference in outcome will be determined with Mann-Whitney U-test

For all outcome measures and statistics, both whole cohort and surgery-specific stratification analysis will be conducted.

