2. INTRODUCTION

Major knee surgery is associated with post-surgery pain. The surgical site is subject to bleeding and inflammation-related fluid build-up in the intraarticular tissues (Holm et al, 2020). Pain may impact negatively on recovery time and active early rehabilitation due to physical impairment that it may cause ((Mizner & Snyder-Mackler, 2005). This in turn may increase hospital length of stay and poor patient reported-outcomes (Moretti et al, 2012; Williams et al, 2013). Many service improvement programmes and techniques have been introduced in knee surgery over the years, including means to reduce intra-articular bleeding, tourniquets and medication (Martin et al , 2014). Initiatives in post-surgical management of patients have been less successful. These include methods such as the use of a cold compress (Morsi 2002), cryotherapy (Adie et al, 2012), elastic bandaging (Hughes et al, 1995) and some types of compression bandaging (Anderson et al, 2008; Charalambides et al, 2005).

Compression bandage therapy is established treatment of venous ulcers and lymphoedema (Franks et al, 2004, Pike 2011). It is hypothesised that the application of this external compression aids venous return and reduces hydrostatic pressure in the leg by (i) improving the efficacy of the calf muscle pump and (ii) moving blood from the superficial to deep venous system, subsequently allowing movement of fluid from the interstitial space. The use of inelastic bandages are preferred in arthroplasty as they have a low, tolerable resting pressure but a more effective activation of the deep venous system and calf muscle pump with ambulation compared to their elastic counterparts (Spence & Cahall, 1996).

The efficacy in total knee arthroplasty is still unclear due to conflicting results in the literature and heterogeneous methodology (Munk et al, 2013; Pinsornsak P & Chumchuen, 2013; Cheung et al, 2014). An acute pain study by Andersen et al (2008) utilised a compression bandage consisting of a double layer of soft padding and an outer elastic adhesive dressing compared with standard bandage in a randomised controlled trial of 48 patients. The intervention group had significantly reduced pain at 8 hours compared to a control group, though the bandage was combined with local anaesthetic infiltration.

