3.1.2 Andoflex TLC Calamine Lite compression bandaging (intervention) arm

As with standard bandaging, the Andoflex TLC Calamine Lite compression bandage will be applied over the routine surgical wound dressing. A foam inner bandage (Andoflex TLC Calamine Lite 2, Milliken Healthcare) is applied from the toe to the groin on the affected leg with minimal overlap. The second layer, which is the actual compression bandage (Andoflex TLC Calamine Lite 2, Milliken Healthcare) is applied at full stretch and with a 50% overlap of bandage to ensure adequate

compression in the application. The mode of action of this two layer compressive bandage kit is of particular practical use, since it is tolerable for patients overnight due to its low resting pressure. Furthermore, it produces high pressure compression with movement to stimulate the calf muscle pump. The bandage is applied from the toes upwards. The application of bandage from thigh to groin requires removal of the tourniquet first and so the leg is kept elevated until the bandaging is complete. There is a training video available on correct application of the bandages: https://www.youtube.com/watch?v=pal0pY_cTRc (Andoflex is known as Coflex in some other countries such as the USA).

The compression bandage has been shown to effect compression for up to a week. To balance compression and comfort, patients are asked to continue wearing the bandage for 5 consecutive days after surgery. The bandages can be removed sooner if the patients find them very uncomfortable (which will be classed as an adverse event) or in the event of any other adverse events that would require their removal – this will be recorded on the Case Report Form and in medical notes. If requested by the patient, they are allowed to return to a hospital clinic to have the Andoflex TLC Calamine Lite bandaging reapplied if for any reason the first set needed to be taken off. To maintain consistency, clinical healthcare professionals who apply a new Andoflex TLC Calamine Lite bandage need to sign a declaration that they have watched the training video and are comfortable complying with the instructions. Full product information on the Andoflex TLC Calamine 2-layer compression system can be found on the Andover Healthcare Inc website https://andoverhealthcare.com/product/coflex-tlc-calamine/

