5.3 Consent and recruitment

Those eligible will be approached and provided with an information pack and consent form, which will be signed to indicate that informed consent has been given. Patients will be given ample time to

consider taking part, more than 24 hours if they wish. The study will be first mentioned at an orthopaedics out-patient clinic visit. The direct healthcare professional will first approach a patient about the study, and after verbal consent by the patient the healthcare professional themselves or a member of the research team can go through the informed consent process.

Patients are also allowed to consent to taking part when first approached as long as the study has been discussed with the patient and they have been given time to read the patient information leaflet and opportunity to ask any questions that they may have. Participants will receive no incentives and consent will be regarded as a process and not a one-off event. Participants are free to withdraw from the study at any time without the need to give any reasons for withdrawal. Their standard of care will not be affected by either declining to participate in the study or withdrawing during participation. Data collected up to the date of withdrawal will be retained for analysis.

Participants will be randomised to either the control bandage group (TaU) or the intervention group (Andoflex TLC Calamine Lite) any time up until the day of surgery.

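### Section 8.3 treats length of stay and post-operative analgesic type as baseline variables and adjusts for them in the secondary regression, although both arise after the bandage is applied

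*Protocol*

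**What the plan says.** Protocol section 8.3 opens with a comparability check: "The average baseline demographics for participants in each group will be compared to ascertain that randomisation has indeed led to comparable distribution of participants". The variables for that check follow: "Sex, age, height, weight, BMI, length of stay, type of anaesthetic for surgery and type of analgesics post-surgery".

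The same section then plans a Cox proportional hazards regression "to investigate the role of bandaging and other covariates (as mentioned above) in post-surgery related pain and knee function". The only variable list above that sentence in 8.3 is the one just quoted. If the reference is meant to reach back to section 8.1, that list also contains length of stay and the post-operative analgesics, and adds the time at which physiotherapy starts.

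On timing, section 5.3 places randomisation "any time up until the day of surgery". Section 3.1.2 says of the intervention: "As with standard bandaging, the Andoflex TLC Calamine Lite compression bandage will be applied over the routine surgical wound dressing". Section 3.1.1 has the control bandage applied as soon as the operation ends, and Table 3 marks bandage application on the day of surgery.

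On mechanism, section 4.1 sets out to show that the bandage reduces post-operative pain. The Introduction, having said that pain hampers recovery and early rehabilitation, adds: "This in turn may increase hospital length of stay".

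**The concern.** A baseline variable is one that the allocated treatment cannot have changed. Length of stay is complete only at discharge, and post-operative analgesics are prescribed after surgery, so neither meets that definition here. Two uses in 8.3 depend on it.

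The first is the check on randomisation. With true baseline variables, differences between arms under sound randomisation are due to chance. With a variable measured under treatment, a difference may be a treatment effect, so it cannot be read as evidence about the allocation.

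The second is the adjusted model. Holding a consequence of treatment fixed removes the part of the effect that passes through it. If an unmeasured factor such as frailty influences both that variable and pain, conditioning on it also adds bias of its own. The bandage coefficient then no longer answers the question of what the bandage does overall.

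**Working it through.** The plan gives no figure for this point, so the check is mainly one of timing and causal order.

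**Step 1, timing.**

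| Item in the 8.3 list | When it is fixed | Before the bandage? |
|---|---|---|
| Sex, age, height, weight, BMI | Before surgery | Yes |
| Type of anaesthetic | By the operation | Yes |
| Length of stay | At discharge | No |
| Type of analgesic after surgery | After surgery | No |

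**Step 2, causal order.** For length of stay, the protocol supplies both links: bandage to pain (4.1) and pain to stay (Introduction). Stay is then downstream of treatment and, for early pain scores, possibly downstream of the outcome itself. For analgesic type, the protocol states no link. That prescribing responds to pain is an inference, and it weakens if prescribing follows a fixed routine.

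**Step 3, what adjustment does, as a linear illustration.** The plan's effect size is reproduced first: 1.5 cm / 2 cm = 0.75 (section 6.1, Table 4). In a linear model:

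adjusted effect = total effect − (within-arm slope of pain on the covariate) × (shift in the covariate caused by the bandage)

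In SD units this is dY − ρ·dM. The inputs ρ = 0.3 to 0.6 and dM = 0.2 to 0.5 SD are assumptions; the protocol gives neither.

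- Low end: 0.3 × 0.2 = 0.06 SD; × 2 cm = 0.12 cm; 0.06 / 0.75 = 8%. The benefit falls from 1.5 to 1.38 cm.
- High end: 0.6 × 0.5 = 0.30 SD; × 2 cm = 0.60 cm; 0.30 / 0.75 = 40%. The benefit falls from 1.5 to 0.90 cm.
- Opposite sign: if stronger analgesia goes with less pain within an arm, ρ is negative for an analgesic-strength covariate. The same formula gives 0.75 + 0.06 = 0.81 to 0.75 + 0.30 = 1.05 SD, or 1.62 to 2.10 cm. Adjustment then inflates the effect.

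**Step 4, no mediation but a shared cause.** Suppose an unmeasured factor raises the covariate by 0.5 SD and pain by 0.5 cm per SD of that factor. The within-arm slope is then 0.5 × 0.5 = 0.25 cm per SD. With a covariate shift of 0.5 SD, the adjusted benefit is 1.5 − 0.25 × 0.5 = 1.375 cm, although none of the effect passes through the covariate.

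A simulation of the linear model (400,000 draws per scenario, shift 0.5 SD) agrees. The adjusted effect was −1.21 cm with 20% of the effect mediated, −0.89 cm with 40%, and −1.39 cm with 0% mediated but a shared cause. Without the covariate, the model returned −1.5 cm up to simulation error in every scenario.

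**Step 5, where it applies.** Section 8.2 compares arms on day-5 pain with a Mann-Whitney test without covariates. The other group comparisons in 8.3 are also unadjusted. Only the regression and the comparability check use the list.

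**The case against.** The strongest case on the other side concerns reach, and much of it stands.

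- A reader might infer that the primary result stands to lose 8% to 40% of its effect. The documents do not support that: the 1.5 cm effect belongs to the day-5 comparison, which is unadjusted.
- The only covariate model planned is a Cox model, which yields a hazard ratio. Centimetre figures from a linear model cannot be the bias in that analysis.
- A reader might infer that a real benefit would be declared failed randomisation and then adjusted away. No rule in the protocol ties adjustment to an observed imbalance, and the unadjusted comparisons are planned in any case. The regression can also be read as exploratory.
- For analgesics, only the type prescribed is recorded, not the amount taken. Neither the effect of the bandage on it nor the direction of the bias is established.
- A reader might wish to strike every operative item from 8.1. Operation length and blood loss during surgery precede the bandage, and describing them by arm is legitimate.

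None of this rescues the classification in 8.3. The back-reference is slightly ambiguous, but both possible lists include the two variables. An exploratory model still misleads if its bandage coefficient is read as the effect of the bandage. Nor is this detail left to an analysis plan: the protocol itself labels these variables as baseline and makes them covariates.

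**Conclusion.** The point holds for the secondary regression and the comparability check. It is firm for length of stay, where the protocol states both links of the causal path. It is less certain for analgesic type, where timing is clear but the effect of the bandage is inferred.

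The adjusted model would not estimate the total bandage effect if the bandage shifts these variables and they are on the path to the outcome, follow from it, or share a cause with it. If the bandage does not shift them, the linear bias vanishes. The size cannot be derived from the document. The 0.12 to 0.60 cm range illustrates the mechanism under assumed correlations and shifts in a linear model, and its direction can reverse for analgesics. The primary analysis and the sample size are untouched. This should be corrected, but it does not threaten the main conclusion of the trial.

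**What to change.** In section 8.3:

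- Remove length of stay and post-operative analgesic type from the baseline comparability list.
- Remove both from the covariate set of the regression, and name the covariates instead of referring back. If the reference was meant to include 8.1, also keep out the time at which physiotherapy starts.
- Use covariates fixed before the bandage is applied. Those already collected include age, sex, BMI, surgery type (by which randomisation is already separated) and the baseline score of the outcome concerned.
- Report length of stay and analgesic type by arm as post-randomisation outcomes.

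In section 8.1, label length of stay, post-operative analgesics and physiotherapy start as post-randomisation data. Operation length and blood loss can stay as descriptive operative data.

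The cost is a wording change in two sections. No data collection, sample size, significance level or primary test changes.

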5.5 Outcome measures

5.5.1 **Primary outcome measures**

To determine the level of operation-site related pain experienced at day 5 post-operation and to compare the average pain scores of patients in the control and Andoflex TLC Calamine Lite arm respectively, through administration of 10 cm visual descriptor scale (VDS) for pain.

The study is powered to detect the established minimal clinically important difference (MCID) of 1.5 cm on a 10 cm VDS pain.

5.5.2 **Secondary outcome measures**

All the outcome measures are summarised in Table 3.

Table 3. Overview of measurements

Weeks	-12 weeks to day of surgery	0 surgery	3 days ^{##}	5 days ^{##}	12 days [#]	6 weeks*	12 weeks *
Application bandage		Х					
straight after surgery							
VDS pain scale (at rest)	Χ		Χ	Χ	Χ	Χ	
VDS pain scale (walking)	Х		Χ	Χ	Χ	X	
McGill pain	Х		Χ	Χ	Χ	X	
questionnaire							
Limb range of motion	Х					X	
KOOS score	Х					X	Χ
Patient satisfaction					Χ	(X, if not	
questionnaire re						returned	
bandaging						yet at 12	
						days)	

^{*} Allowed to be up to 2 weeks early or late # Allowed to be up to 3 days early or late ## Allowed to be up to 1 day early or late

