6. SUBJECTS

6.1 Anticipated number of research subjects

The sample size calculation does take into account a 20% patient attrition rate (withdrawal and loss to follow-up), since this involves a study with multiple time points for data collection up to 12 weeks. Patients will be recruited from the adult (age 18+) population routinely seen by the evaluating clinical staff members. The primary outcome measure is based on knee/leg (ie wound site) pain experienced 5-days post-surgery based on the VDS pain scale 'at rest'. The hypothetical difference in pain perception is 1.5 on a 10 cm scale which equates to a significant 'minimally clinically important difference' for pain (Kelly 2001; Lee et al 2003; Tashjian et al 2009). The values and differences observed in the ROBOT trial will be used for reference.

The non-parametric two-sided Mann-Whitney u-test is applied because the data is ordinal; 80% power and 5% significance is also applied. A priori power calculations using GPower 3.1 software, result in the following sample size summarized in Table 3.

Analysis will be performed on an intention-to-treat basis, although the number of days that a participant has worn a bandage will be recorded.

Data will be analysed as one cohort and also stratified by surgery type (knee replacement, osteotomy) in the resulting analysis.

Table 4, Sample size calculation

	Mean pain score at 5 days post-op	Standard Deviation
Arm A (hypothetical)	5.0	2

Arm B (hypothetical)	3.5	2			
	Power beta of 80%, Alpha p-value of 0.05, Effect size 0.75 Sample size required without any drop-out: 62 samples.				
	Sample size with 20% attrition rate included: 74				
	Total of 74 patients per surgery type:				
	- 37 Patients to receive non-compression bandaging				
	 37 Patient to receive Andoflex TLC Calamine Lite dual-layer compression bandaging 				
	Therefore total is: - 74 knee replacement cases - 74 osteotomy cases				
	Overall trial sample size: 148				

The CONSORT guidelines require a statement on the number of patients assessed for eligibility (Schulz, Altman & Moher 2010). The number of patients screened but who did not meet the inclusion criteria or who declined to participate will be recorded, as will any patients who are lost to follow-up (Appendix 3).

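### Section 8.3 names Cox regression for pain and knee function, which the protocol measures only as scores at fixed visits, so the one covariate-adjusted analysis is mis-specified

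*Protocol*

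**What the plan says.** Section 8.3 first lists the characteristics to be compared between arms: age, sex, BMI, height, weight, anaesthetic type, post-surgery analgesic type and length of stay. It then names two-group tests (t-test, Mann-Whitney or chi-squared) for the outcomes. After that it states: "Cox proportional hazards regression analysis will be conducted to investigate the role of bandaging and other covariates (as mentioned above) in post-surgery related pain". The sentence continues to a second outcome, so its full scope is "in post-surgery related pain and knee function".

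The outcomes it refers to are defined elsewhere:

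- **Pain, main measure.** Section 8.2 compares average pain scores at day 5 "through administration of 10 cm visual descriptor scale (VDS) for pain". It adds: "Three days, 12 days and 6 weeks post-surgery will also be analysed". Table 3 schedules VDS both at rest and walking.
- **Pain, second measure.** At the same visits, "pain perception will also be measured using the short form McGill pain questionnaire".
- **Type of data.** Section 6.1 says: "The non-parametric two-sided Mann-Whitney u-test is applied because the data is ordinal; 80% power and 5% significance is also applied".
- **Knee function.** The summary and section 8.3 name KOOS and goniometer range of motion. Table 3 places KOOS at baseline, 6 weeks and 12 weeks.

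**The concern.** A Cox model describes the rate at which an event occurs over time. Its response is a time to that event, and its result is a hazard ratio. The outcomes named in the sentence are how much pain a patient reports, or how well the knee works, on a given visit. The visit time is set by the schedule, and the information lies in the score.

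The Cox sentence is the only place in the plan where the bandage effect is examined together with covariates. Everything else is a two-group comparison, overall or within surgery type. If the model does not fit the outcomes, the trial has no usable plan for an adjusted effect. An analyst would then have to choose the model, or invent an event, at a point when data may already have been seen. Section 9 foresees an interim analysis at half the sample.

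**Working it through.** The protocol gives no hazard ratio, event count or event definition for the Cox model, so there is no Cox figure to reproduce. The check compares the model with the outcome definitions, and then asks whether any reading of the sentence rescues it.

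**1. Outcome definitions against what a Cox model needs**

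| Outcome | Form of the data | Post-operative visits | Event, threshold or time origin defined? |
|---|---|---|---|
| VDS at rest, VDS walking | position on a 10 cm scale | days 3, 5, 12; week 6 | none |
| Short-form McGill | questionnaire score | days 3, 5, 12; week 6 | none |
| KOOS | questionnaire score | weeks 6 and 12 | none |
| Range of motion | goniometer measurement | week 6 in Table 3; weeks 6 and 12 in the summary; week 12 in 8.3 | none |

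The only event-type outcomes are readmission, wound infection and PE/DVT. The plan treats these as a descriptive safety overview, and the Cox sentence does not name them.

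**2. What the trial is sized for**

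Inputs from Table 4 and section 6.1: means 5.0 (Arm A) and 3.5 (Arm B), SD 2, two-sided alpha 0.05, power 80%, Mann-Whitney test.

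- Effect size: (5.0 − 3.5)/2 = 0.75, as stated.
- Two-sample t-test size: 28.9 per arm.
- Mann-Whitney size: divide by the asymptotic relative efficiency 3/π = 0.955. This gives 28.9/0.955 = 30.3, so 31 per arm and 62 in total.

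This reproduces the stated 62 per surgery type before drop-out. The design therefore rests on a comparison of scores and not on a number of events.

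**3. Three ways to read the Cox sentence**

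(a) *Visit time as the time variable.* Patients share nearly the same times by design (within 1 day at days 3 and 5, by the footnote to Table 3), and the score does not enter as the response. This does not address pain or function.

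(b) *Time to a threshold, such as pain below a cut-off.* This is a legitimate analysis, but the protocol gives no threshold. With four post-operative pain visits and two KOOS visits, the event would be known only to fall between visits. It would also be a new outcome.

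(c) *The score itself in place of time.* This can be fitted, because the partial likelihood uses only rank order. The protocol's planning values show what it would deliver. Assume normal scores with those means and SD. The hazard at score x is φ(z)/{2[1 − Φ(z)]}, with z = (x − mean)/2.

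- At x = 2 cm: Arm A 0.1295/(2 × 0.9332) = 0.069; Arm B 0.3011/(2 × 0.7734) = 0.195; ratio about 2.8.
- At x = 7 cm: Arm A 0.2420/(2 × 0.1587) = 0.763; Arm B 0.0863/(2 × 0.0401) = 1.08; ratio about 1.4.

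One constant shift of 1.5 cm gives a ratio that halves across the scale. Under the plan's own working values, hazards are not proportional, and a single hazard ratio does not translate into the 1.5 cm difference the trial is about.

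**4. Covariates**

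Section 5.3 randomises at any time up to the day of surgery. Length of stay and post-surgery analgesics come later and could be affected by the bandage. Adjusting for them could remove part of the treatment effect or bias it.

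**The case against.** Four points can be made for the plan.

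- **Scope.** The primary analysis is the day 5 Mann-Whitney test, and every secondary outcome also has a usable two-group test. If the Cox sentence were deleted, the randomised comparisons would survive unchanged. This stands. A reader might infer that the trial cannot answer its main question, and the documents do not support that.
- **Feasibility.** Cox regression does not require censored observations and can be fitted to ranked scores. With proportional hazards and no ties, a hazard ratio h corresponds to a probability of h/(1 + h) or 1/(1 + h) that a score in one arm exceeds one in the other, which is the quantity a Mann-Whitney test addresses. This also stands. It would be too strong to say that the model cannot be run or that its output has no meaning. It remains true that the protocol does not say this is intended, and that proportionality fails under its own planning values.
- **Units.** The Mann-Whitney test does not report centimetres either. That is correct, but it is named as a test for comparing groups. The regression is meant to describe the role of bandaging and covariates, so the scale of its estimates matters more.
- **Detail left to the SAP.** An SAP could define an event. However, the protocol does not leave the model open: it names one and attaches it to outcomes it defines only as scores. An SAP could cure this only by changing the model or adding an outcome.

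**Conclusion.** The named model does not match the named outcomes, and this is wrong as written, not just missing detail. It affects the adjusted analysis of all pain and function measures: VDS at rest and walking, McGill, KOOS and range of motion, both in the whole cohort and by surgery type, since section 8.3 applies its statistics to both. The size is a count of affected analyses. No bias or loss of power can be computed, because the protocol gives no Cox inputs.

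The primary day 5 test, the sample size of 62 per surgery type before drop-out and the unadjusted secondary tests are not affected.

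The main conclusion rests only on the protocol's outcome definitions. The hazard ratios of 2.8 and 1.4 additionally assume normal scores with the planning means and SD. They are an illustration, and the conclusion does not depend on them.

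**What to change.** Replace the Cox sentence in section 8.3 with a regression for scores:

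- **Outcomes.** VDS at rest, VDS walking, McGill, KOOS and range of motion. State which visits apply to range of motion, since Table 3, the summary and section 8.3 differ.
- **Model.** ANCOVA at a given visit or a linear mixed model across visits. Because section 6.1 calls the pain data ordinal, a proportional-odds model is an equally sound choice for pain. Any of these is acceptable if it is fixed in advance.
- **Terms.** Arm, baseline value of the same measure, surgery type, and the listed covariates that are settled before randomisation, such as age, sex and BMI. BMI is derived from height and weight, so all three need not enter together.
- **Not adjusted for.** Length of stay and post-surgery analgesics, which can be reported by arm instead. Anaesthetic type may be decided after randomisation, so its use needs a stated reason.
- **Reporting.** Adjusted effects with 95% CI: mean differences in cm, points or degrees, or odds ratios under proportional odds.

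If a time-to-event question is truly wanted, keep Cox and define the event, time origin and censoring rule.

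Either change should be made before any data are analysed, including the interim analysis at half the sample. It costs a few sentences in section 8.3 and an amendment, with no new data and no change in sample size.
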